Building on the development of the SC-TF-CBT model,[4-7] this R01 application examines how to optimize the efficiency and cost-effectiveness of SC-TF-CBT, a personalized adaptive intervention, under “real world” settings. The proposed research is in line with NIMH research priorities for trials that foster personalized mental health care, incorporating tailoring variables to match interventions to patient needs, and to optimize interventions.[8] Consistent with RFA-MH-15-320, this application proposes to test a new service delivery approach compared to existing practice and to elucidate mechanisms of change within two-trauma focused interventions with the goal of improving the value and efficiency of trauma-focused treatment compared to standard practice. This project has the potential to improve the accessibility, efficiency, and effectiveness of clinical practice, while reducing the cost of treatment and reducing the societal impact of childhood PTSD.

**Aim 1:** To examine the relative efficacy of SC-TF-CBT (e.g., starting with Step One parent-led, therapist-assisted treatment and then either maintenance or Step Two TF-CBT) versus standard TF-CBT (e.g., therapist-led treatment).

**1.1. Hypothesis:** Given the second-stage treatments provided (maintenance, TF-CBT), children in SC-TF-CBT will demonstrate comparable improvements to children in standard TF-CBT in: (a) child outcomes: PTSD symptoms (PTSS) and functional impairment (primary outcomes), internalizing and externalizing behaviors, PTSD severity, and global improvement; (b) acceptability and satisfaction levels; and (c) parent secondary outcomes: parenting stress, depression, and PTSD symptoms.

**1.2. Hypothesis:** Children in SC-TF-CBT and standard TF-CBT will continue to have comparable improvements in child and parent outcomes throughout the 6- and 12-month follow-up period.

**Aim 2:** To examine tailoring variables that could be used to individualize (i.e., tailor) the decision of which children should be assigned at baseline to SC-TF-CBT versus standard TF-CBT.

**2.1. Hypothesis:** Children with high internalizing problems or high perceived critical life events are less likely to respond to first-stage Step One.

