### **c.8.3. Specific Analyses for the Individual Study Aims**

**Primary Aim 1:** For the primary and secondary hypotheses, one-sided tests for non-inferiority will be applied as our goal is to show that the performance of the children in SC-TF-CBT will demonstrate comparable improvements to children in standard TF-CBT. For this non-inferiority test, the null hypothesis is written as  $H_0: \mu_1 - \mu_2 > r^*$ , where  $\mu_1$  denotes the average improvement in standard TF-CBT and  $\mu_2$  denotes the average improvement among children in SC-TF-CBT, and  $r^*$  represents the clinically significant difference expressed as common standard deviation units. The test will be applied to child outcomes, acceptability/satisfaction levels and parent outcomes that will be measured at post-treatment and at 6- and 12-month follow-up respectively.

Rejection of the null hypothesis will indicate that treatment outcomes of SC-TF-CBT are comparable to those from standard TF-CBT. For child and parent outcomes only, we will further apply GLM with repeated measures to detect whether the two treatment groups perform differently at any one time point. We will also document the percentage of responders to Step One and numbers and reasons for trigger and switch.

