**c.9. Sample Size Considerations and Power Analyses.** We will enroll a total of N=216 subjects with a 1:1 randomization between SC-TF-CBT and standard TF-CBT. Based on our successful track record in obtaining post and follow-up data in our R34 SC-TF-CBT trial (only 3.77% missing post- data, and 6.1% missing 3-mo. follow-up data, N=53), and the PIs previous child trauma clinical trial with a 1-year follow-up (8.57% attrition), we conservatively anticipate 15% attrition at post-assessment resulting in 184 subjects (92 per group) and a 10% lost to follow-up at 6- and 12-months resulting in 166 subjects (83 per group) and 150 subjects (75 per group), respectively. Sample size requirement was determined by CEA for Primary Aim 4 and it also provides sufficient power for Primary Aims 1 to 3 under various assumptions. **Primary Aim 1**, Hypothesis 1.1, the study will have 80% power to show that SC-TF-CBT is at least as effective as standard TF-CBT. This assumes an alpha of .05, sample size of 92 per group after attrition and a difference of 0.41 SD units or less as unimportant. We expect to maintain the same power of 80% in testing the hypothesis (1.2.) that focuses on the outcomes at follow-up (6- and 12-months). Though we may lose an additional 10% of participants at each follow-up point, reduction in measurement error through repeated measures and use of multiple imputation method will mitigate the sample size loss. For **Primary Aim 2**, 80% power will be achieved for detecting responding rates difference between 62% and 30%, 72% and 40%, or 80% and 50%. This assumes that we divide the patients into two equal size groups based on the tailoring variable value with a total of 92 patients (SC-TF-CBT condition only). For **Primary Aim 3**, we will have >80% power to detect a small to moderate effect (0.29) in a unidirectional bivariate latent different score model with complete longitudinal observation for the 184 children under both conditions (for analyses involving CPTCI, the detectable effect size is 0.33). For the secondary hypothesis 3.2., we have moderate power (.57) to detect different strengths of the unidirectional prediction between the two conditions (e.g., 0.15 vs 0.45 or .00 vs .30; for the CPTCI, the power for the same comparisons is .55). For **Primary Aim 4**, the study will have 80% power to detect cost differences between SC-TF-CBT and standard TF-CBT, assuming medium effect size (.5), an alpha of .05 and sample size of 92 per group. The sample size will also be sufficient to maintain 80% power to detect a medium effect size for children with low values for the tailoring variable, and to detect a large effect size for children with high values.

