While it is possible that the viewing the brief segments of the child's session via video will affect the parent's distress level, parental distress about the child's trauma and depression did not mediate the effect of treatment (TAU and TF-CBT) on child PTSD symptoms, although there was an effect on child depression. Sharing and discussing with the parent what the child completed in therapist-led session is current protocol for both treatments, and similar procedures have been used in previous trauma-focused clinical trials with children 3 to 12 (PI: [name], R34MH070827-01A1; 1RC1MH-088969-01). Research has shown that parent distress about the child's trauma improved during participation in TF-CBT. If parents experience discomfort during the treatment, we will provide supportive counseling as part of the treatment. However, if parent distress continues and psychiatric attention is needed, parents will be provided with a list of community mental health resources. Parent participation in individual therapy outside of the study is not an exclusion criterion. If a parent participates in other therapy we will document this but will not exclude parents who are participating in their own therapy since we are not providing parent-focused mental health treatment. The treatment is child-focused although it is likely that some parents will benefit psychologically from their child's participation in treatment as well as from the supportive counseling that will be provided in both treatment arms.

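### For parent outcomes, passing the non-inferiority test cannot by itself support a claim of comparable improvement, because nothing requires the standard TF-CBT arm to have improved

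*Combined protocol and SAP*

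**What the plan says.** Hypothesis 1.1 in the Specific Aims states that SC-TF-CBT will give improvements comparable to those of standard TF-CBT. Part (c) covers "parent secondary outcomes: parenting stress, depression, and PTSD symptoms", and hypothesis 1.2 carries the claim to 6 and 12 months.

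For Primary Aim 1, c.8.3 says that "one-sided tests for non-inferiority will be applied". The null is that average improvement under standard TF-CBT exceeds that under SC-TF-CBT by more than the margin. On scope: "The test will be applied to child outcomes, acceptability/satisfaction levels and parent outcomes that will be measured at post-treatment", and also at the two follow-ups. On interpretation: "Rejection of the null hypothesis will indicate that treatment outcomes of SC-TF-CBT are comparable to those from standard TF-CBT".

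Section c.9 sets the margin by treating "a difference of 0.41 SD units or less as unimportant". The analysis amendment of 2.11.2022 keeps 0.41, moves to a 2.5% alpha, and gives the PCL-5 its own margin of 8.8 points, based on an expert panel and prior adult studies. The protocol's only PCL is the parent PCL-C (c.6.2), so that margin is presumably for parent PTSD symptoms.

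On parents themselves, c.2.2 requires willingness and ability to take part and sets no minimum level of stress, depression or PTSD symptoms. Section 5.1.1 c explains that parents in their own therapy are not excluded "since we are not providing parent-focused mental health treatment". It calls the treatment child-focused and expects psychological benefit in some parents.

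**The concern.** A non-inferiority test compares two arms. It supports a statement that both arms gave similar benefit only when there is reason to think the comparator gave a benefit larger than the margin. For the parent outcomes the documents offer no such reason. No cited or assumed TF-CBT effect on parents underlies the 0.41 SD margin, and the 8.8-point margin comes from adult work while these parents are unselected.

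No other Aim 1 analysis fills the gap. The repeated-measures GLM in c.8.3 and the linear mixed model in the amendment are both described as looking for differences between treatments. Neither comes with a rule about change within the standard arm.

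If parents change little in either arm, the plan as written would report the parent part of hypotheses 1.1 and 1.2 as supported. A reader would then take it that parents improved about equally under both treatments when the data had not shown that they improved at all.

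**Working it through.** **Inputs.** Margin 0.41 SD and 92 per group (c.9). One-sided 2.5%, 183 randomised (91 and 92) and 27.87% attrition (amendment). 183 × (1 − 0.2787) = 132 remaining, or 66 per arm if losses were even, which is an assumption. As in c.8.3, μ₁ and μ₂ are the average improvements under standard TF-CBT and SC-TF-CBT, here in SD units.

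**Formula.** With n per arm and a normal approximation, the chance of declaring non-inferiority is

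P = Φ( (0.41 − (μ₁ − μ₂)) × √(n/2) − z ), with z = 1.96 at one-sided 2.5% and 1.645 at one-sided 5%.

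**The plan's own figure.** Section c.9 says "the study will have 80% power to show that SC-TF-CBT is at least as effective as standard TF-CBT". With no true difference and n = 92, 0.41 × √46 = 2.781.
- One-sided 2.5%: Φ(2.781 − 1.96) = Φ(0.821) = 79.4%. Exactly 80% needs 94 per group.
- One-sided 5%: 87.2%. Here 80% needs only 74 per group.

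The stated 80% therefore reproduces at one-sided 2.5%, the level the amendment adopts, which is used below.

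**One parent outcome, SC-TF-CBT having no effect (μ₂ = 0).**

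| Standard TF-CBT improvement μ₁ | 92 per arm | 66 per arm |
|---|---|---|
| 0 | 79% | 65% |
| 0.1 SD | 56% | 43% |
| 0.2 SD | 30% | 23% |
| 0.3 SD | 11% | 9% |

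For example, μ₁ = 0.2 and n = 92 gives (0.41 − 0.20) × √46 = 1.424, and Φ(1.424 − 1.96) = Φ(−0.536) = 30%. The first row at 92 per arm is the plan's power itself: the test sees only μ₁ − μ₂, and two arms that both do nothing have the same difference as two arms that both work equally well.

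**All three parent outcomes together.** Hypothesis 1.1(c) lists the three jointly. Using a trivariate normal with correlation .5 (assumed) and 0.41 SD for each, at 92 per arm all three pass with probability 60%, 30% or 10% when μ₁ is 0, 0.1 or 0.2 SD.

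**PCL-5 at 8.8 points.** The documents give no SD, so a range of 10 to 20 points is assumed. Since 8.8 / 0.41 = 21.5, the 8.8-point margin is wider than 0.41 SD for any SD below 21.5 points. With no effect in either arm, the test passes 84.5% of the time (SD 20) to more than 99.9% (SD 10) with 91 and 92 per arm, and 71.5% to 99.9% with 66. With a 5-point improvement under standard TF-CBT and none under SC-TF-CBT, it passes 25% to 73% of the time with 91 and 92.

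**The case against.** The strongest reply is that the test does what it says. With no effect in either arm SC-TF-CBT really is non-inferior, and at a standard-arm benefit of 0.1 to 0.3 SD the true difference lies inside what c.9 calls unimportant. A reader might take the percentages above as false-positive rates. They are not: each is the chance of a conclusion that is correct under the stated margin. This stands, and it confines the point to the step from comparable to comparable improvement.

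A reader might also infer that neither treatment addresses parents. The documents do not support that. Section c.3.1 lists parent and conjoint sessions and parenting skills within TF-CBT, Step One is parent-led, and 5.1.1 c mentions supportive counselling in both arms and earlier evidence that parental distress about the trauma improved during TF-CBT. The remark about parent-focused treatment explains an eligibility decision. The inference is weakest for parenting stress. Nor do the documents give baseline parent scores, so a floor effect is possible but not shown.

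It is tempting to quote the chance that at least one of three outcomes passes (80% and 53% at standard-arm effects of 0.1 and 0.2 SD, 92 per arm, same correlation). Hypothesis 1.1(c) contains no such any-of-three rule, so that figure is set aside.

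A further temptation is to gate every outcome on the standard arm's improvement having a lower confidence limit above the margin. Nothing here shows a problem with the child outcomes. Table 1 has no baseline for the CSQ or CGI-I, so the gate would be undefined for them. It is also severe: with an assumed pre-post correlation of .5 to .7, an arm truly improving by 0.5 SD would pass only 14% to 20% of the time at 92 per arm.

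Last, parent outcomes are secondary and the amendment is written after the fact. Both are true and limit the weight of the point.

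**Conclusion.** The concern holds, limited to the parent parts of hypotheses 1.1 and 1.2. The between-arm test is sound, but passing it does not show that parents improved comparably, because the margin may be as large as or larger than anything standard TF-CBT does for parents. Whether that happened cannot be told from the documents. What can be told is that the plan has no step that would reveal it, and that the conclusion would be reached about 79% of the time per outcome at 92 per arm (65% at 66) with no change in either arm.

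These figures rest on a normal approximation, equal SDs, even attrition for the 66, and a correlation of .5 with a common 0.41 SD margin for the 60% joint figure. A mixed model using partial data would probably fall between the 92 and 66 columns. That the PCL-5 margin belongs to the parent measure is an inference. The primary child outcomes, the CSQ and the CGI-I are unaffected.

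**What to change.** In c.8.3 and the amendment, for parenting stress, parent depression and parent PTSD symptoms only:

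1. Report the between-arm difference with its confidence interval beside each arm's change from baseline, at each assessment.
2. Draw no non-inferiority or comparable-improvement conclusion where the standard TF-CBT arm did not itself improve. State the criterion used; a simple one is that the interval for that arm's mean change lies wholly on the improvement side of zero.
3. Where the standard arm improved by less than the margin (0.41 SD, or 8.8 points for the PCL-5), state that the margin does not exclude zero benefit from SC-TF-CBT.
4. Add the same estimates, as a descriptive analysis, in parents above the scale's clinical cut-off at baseline.
5. State that pre-post change is a necessary check and not proof of efficacy: there is no untreated arm, so natural recovery and regression to the mean are included in it.

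The cost is wording and a few table rows, with no new data. Some secondary parent outcomes may lose a non-inferiority label. Because the amendment describes analyses already done, the change must be labelled post hoc.

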If a child's symptoms worsen, whether the deterioration is linked to the treatment or not, we will discuss with the parent clinically appropriate alternatives, such as increasing therapist-directed therapy sessions during Step One (additional sessions are included in the protocol for situations where children need more therapy), stepping up to Step Two to receive therapist-directed TF-CBT, having a child undergo psychiatric evaluation to determine mental health status, or discontinuing the study and engaging community resources for additional help. Two additional therapy sessions are included in the study protocol for those situations where crises or worsening of symptoms occur (examples may include sexual aggression, danger to self or other). If clinical worsening occurs during treatment, the therapist will discuss this in team meetings. The therapist, parent and child (ages 7-12) will complete the CGI-I at each visit. As used in our pilot studies on Stepped Care TF-CBT, clinical worsening is operationalized as a therapist, parent, child or IE rating of 8 ("very much worse"), 7 ("much worse") or three consecutive ratings of 6 ("minimally worse") on the CGI-I. Three consecutive ratings of minimally worse instead of one rating of minimally worse was stated because it is possible that some children may exhibit some regression when processing the trauma narrative, thus resulting in a temporary minimally worse rating. As previously planned, the parent, child, and IE will complete the CGI-I at post-treatment and follow-up. The therapist will complete the CGI-I after every face-to-face session and one time a week via phone sessions during

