Step One to consistently monitor possible clinical worsening. If clinical worsening occurs, the PI will consult with [name] about the appropriate course of treatment, which may include additional sessions, having a child undergo psychiatric evaluation to determine their mental health status and/or discontinuing the study and seeking additional help from community resources. If an additional session is indicated, the therapist will plan for the individualized session during the weekly team meeting so that an individualized targeted plan for the session(s) can be developed based on the noted concern(s). Including additional sessions does not compromise the integrity of the intervention, while balancing the well-being of participants. On balance, the majority of families in our pilot studies on Stepped Care TF-CBT and standard TF-CBT reported symptom reduction and improvement in functioning following participation.

[name]. Professor and Rothman Endowed Chair, Director, Rothman Center for Pediatric Neuropsychiatry at the University of South Florida has agreed to be involved as an independent consultant who would be available to consult with the PI to make judgments about the appropriate course of treatment for children with ratings of clinical worsening. [name] will not know treatment assignment. [name] worked with [name] on the NIMH R34 Stepped Care for Young Children study in this capacity where she reviewed cases with clinical worsening (4 occurrences of 53 children enrolled in treatment) or clinical concerns (5 occurrences of 53 children enrolled) such as encopresis, passive suicidal ideation, or inappropriate boundaries with other children. [name] also met quarterly with Drs. [name] (PI) and [name] (Co-I) to discuss tolerability and safety. Through this work, Drs. [name] and [name] have established a strong working relationship. [name] (Co-I) also has a long collaborative relationship with [name] in the Departments of Pediatrics and Psychiatry at the Rothman Center for Pediatric Neuropsychiatry. [name] is board certified in child and adolescent psychiatry and general psychiatry, has a Master's degree in Clinical Investigation, and has considerable experience conducting federally-funded clinical trials with children (e.g., 1R01MH078594-01; see [name] biosketch).

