### **Procedures for suicidal ideation**

Children exposed to trauma may experience suicidal ideation which may be reported at baseline and throughout treatment. Following is the plan to monitor suicidal ideation:

Suicidality is a study exclusion: “**3**) Child or parent is suicidal. A delayed entry once the parent or child is stabilized (> 6 months post suicidal) and not having suicidal ideation will be allowed if appropriate.” As stated in the application, parents will be screened at baseline using the SCID (First, Spitzer, Miriam, & Williams, 2002) for suicidal ideation and suicidality. The IE will administer the semi-structured interviews about child suicidal ideation using the DIPA ([name] & Haslett, 2010) or ADIS (Silverman & Albano, 1996) during the baseline, mid-treatment, post-treatment, 6- and 12-month follow-up. We will use the specific questions in the depression modules that inquire about suicidal thoughts, plans and past attempts. As with our pilot trials, if the answer is yes to any of these questions, we will inquire about the specific plans, time of occurrence, frequency, details of attempts, and current ideation. If the child is actively suicidal we immediately will make the appropriate referral for further evaluation and potential hospitalization. The community-based agencies are already well-trained in procedures when a patient is suicidal (i.e., the Crisis Center of Tampa Bay hosts the 211 emergency line and also has an ambulance service that transports suicidal patients), but we will provide additional training and the PI will be notified immediately. Parents will also be provided with appropriate community resources in instances of child or parent suicidality. Similar to our R34 study, [name] will consult immediately with [name] in cases of suicidal ideation and suicidality (although consultation in cases requiring immediate attention such as hospitalization may occur after safety precautions have occurred). For children who are enrolled in the study, the therapist providing treatment will be made aware of any reported suicidal ideation so that the clinician can work with the child and family to provide appropriate intervention and monitoring (see monitoring plan below).

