### **Data and Safety Monitoring Board**

In addition to the above plans for monitoring and ensuring patient safety, we will have a Data and Safety Monitoring Board (DSMB) that will review the study twice a year for the purpose of monitoring subject safety and data integrity. The board will include four faculty members with experience in clinical trials research with vulnerable pediatric populations, including an expert in clinical trials in pediatric PTSD, a biostatistician with pediatric clinical trials experience, a child psychiatrist experienced in psychosocial clinical trials, and a clinical child psychologist with expertise in childhood anxiety. Individuals on the DSMB will not be affiliated with the study.

Specifically, the Monitoring Board will be responsible for:

- 1) Reviewing the research protocol and plans for data and safety monitoring.
- 2) Monitoring adverse event reports, study progression, and data quality issues every 6 months. Evaluating the progress of the trial may also consider factors external to the study when interpreting the data, such

as scientific or therapeutic developments that may have an effect on the safety of the patients or the ethics of the study.

- 3) Inquiring for further information as necessary to accomplish the mission.
- 4) Maintaining confidentiality during all phases of the trial including monitoring, preparation of interim results, review and response to monitoring recommendation,
- 5) Generating a report that will be provided to the PI and the IRB.

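### Clinical worsening, child suicidal ideation and adverse events are collected in both arms but never compared by arm, so a moderate excess in the stepped arm could sit under a finding of comparable means

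*Combined protocol and SAP*

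**What the plan says.** **Collection.** Section 5.1.1.c (Potential Risks) gives an event definition: "clinical worsening is operationalized as a therapist, parent, child or IE rating of 8", or of 7, or three consecutive ratings of 6, on the CGI-I. For the pilot it reports "clinical worsening (4 occurrences of 53 children enrolled in treatment". Under the suicidal ideation procedures, "The IE will administer the semi-structured interviews about child suicidal ideation" at baseline, mid-treatment, post-treatment, 6 and 12 months. Section 5.1.2.b grades complaints from mild to serious, and the independent evaluator (IE) rates relatedness to the study.

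**Use.** Worsening is handled case by case, with a consultant who does not know the assigned arm. Adverse events go to the IRB and NIMH. The Data and Safety Monitoring Board's duties include "Monitoring adverse event reports, study progression, and data quality issues every 6 months". No comparison between arms is specified for the board.

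**Analysis.** Under Aim 1 in c.8.3, "one-sided tests for non-inferiority will be applied as our goal is to show" comparable improvement. The hypothesis concerns average improvement, and the margin "represents the clinically significant difference expressed as common standard deviation units". On scope: "The test will be applied to child outcomes, acceptability/satisfaction levels and parent outcomes that will be measured at post-treatment" and at 6 and 12 months. Hypothesis 1.1 lists global improvement among the child outcomes. The only event-type summary in Aim 1 covers Step One responders and trigger-and-switch cases, which exist in the stepped arm alone. The 2022 amendment changes the model and alpha for Aim 1 and adds no safety comparison.

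**The concern.** The trial asks whether a lower-intensity, parent-led treatment can safely come first. A natural harm question is whether more children get worse along the way. The plan holds the data to estimate that, yet as written it would report only differences in means.

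A mean blends a worsened minority with an improved majority. If the share who worsen rises moderately, the mean moves little, and a margin of 0.41 SD can absorb it. Later means may be affected further. Children who worsen may be given extra sessions or stepped up, and those who worsen at post-treatment or during follow-up are offered booster sessions, so some follow-up scores come after added care. A count of worsening events, recorded as they occur, is less exposed to this.

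**Working it through.** **1. The plan's own figure.** Section c.9 states 80% power: "This assumes an alpha of .05, sample size of 92 per group after attrition and a difference of 0.41 SD units or less as unimportant". For a one-sided test of two means with SD 1 and no true difference, power = Φ(0.41/√(2/n) − z).
- n = 92, one-sided 0.025: 0.41/0.1474 − 1.96 = 0.82, giving 79.4%.
- n = 92, one-sided 0.05: 87.2%.

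The stated 80% therefore matches one-sided 2.5%, which is also the amended alpha. I use 2.5% below.

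**2. Sample sizes.** The planned number after attrition is 92 per arm. The amendment reports 183 randomised (91 and 92) and 27.87% attrition: 183 × 0.7213 = 132, or 66 per arm if losses are equal (assumed). At 66 per arm, power with no true difference is 65.4%. The amended repeated-measures model may use partial data, so I treat 92 and 66 as a range.

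**3. Worsening rate.** The pilot gives 4/53 = 7.5% (exact 95% CI 2.1% to 18.2%). This counts occurrences, possibly not distinct children. It uses the any-rater definition and is not split by arm. At 91 per arm it implies 91 × 0.0755 ≈ 7 children.

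**4. Effect on the mean test.** Assume that the stepped arm's rate doubles to 15.1%, that each extra worsened child ends d SD lower, and that the arms are otherwise equal. The documents give neither the doubling nor d. Mean shift = 0.0755 × d, and P(non-inferior) = Φ((0.41 − shift)/√(2/n) − 1.96).

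| d (SD) | Mean shift (SD) | n = 92 | n = 66 |
|---|---|---|---|
| 0 | 0 | 79% | 65% |
| 1 | 0.08 | 62% | 48% |
| 1.5 | 0.11 | 52% | 40% |
| 2 | 0.15 | 42% | 32% |
| 3 | 0.23 | 24% | 18% |

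Letting the mixture inflate the stepped-arm variance, with the margin held at 0.41, gives 61% to 38% at 92 and 47% to 29% at 66 for d from 1 to 2.

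The largest observed deficit that still passes is 0.41 − 1.96 × √(2/n): 0.12 SD at 92 and 0.07 SD at 66. A large excess would therefore usually make the test fail; the gap concerns moderate excesses.

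**5. What a direct comparison would deliver.** Half-width = 1.96 × √(p1q1/n + p2q2/n).
- n = 91: 7.7 points if both arms are at 7.5%; 9.1 points at 7.5% against 15.1%.
- n = 66: 9.0 and 10.7 points.

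Power to detect the doubling at two-sided 5% is 36% at 91 per arm and 28% at 66. This is an estimate with an interval, not a powered test.

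**The case against.** The strongest reply is that worsening already enters the analysis. The CGI-I defines it, and global improvement is an Aim 1 outcome tested by arm at three time points, with a further repeated-measures comparison. Section c.8.2 also promises descriptive and graphical summaries for all randomised patients. That stands to this extent: a reader might infer that nothing in the plan could reveal harm in the stepped arm, and the documents do not support so strong a reading. But the ratings enter as an average, the defined worsening event is never an endpoint, and the descriptive sentence goes on to baseline and site balance without naming a safety variable.

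Oversight is also real. The board is independent, includes a biostatistician, meets twice a year and may ask for more information. It would be wrong to infer that safety is unmonitored. These provisions protect individual children and trial conduct; none of them specifies an estimate of a difference between arms.

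Three technical objections stand and shape the fix.
- At 66 per arm the illustration fails non-inferiority more often than it passes, and each figure covers one outcome at one time point.
- Table 1 marks the CGI-I at week 6 without naming the rater, while 5.1.1.c names the IE only at post-treatment and follow-up. Week 6 also falls at the end of Step One but mid-course in standard TF-CBT, where the protocol expects some temporary regression around the trauma narrative.
- The amendment is written in the past tense and cites the non-inferiority results, so any comparison added now is probably post hoc.

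**Conclusion.** The point holds as an omission from the analysis plan. Events that bear directly on the safety of starting with less intensive care are collected in both arms and compared in neither c.8 nor the amendment. Under the assumed doubling and a penalty of 1 to 2 SD, a comparable result on means remains quite possible, at 62% to 42% with 92 per arm and 48% to 32% with 66. Those figures rest on a pilot rate of uncertain fit and on two assumptions the documents do not supply; they show that masking can happen, not how likely it is here.

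A reader might go further and infer that stepped care does worsen more children. Nothing in the documents says so: the pilot occurrences are not split by arm, and the definition covers deterioration whether or not it is linked to treatment. The change is worth making because it is cheap and bears on what a claim of comparability can say about harm.

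**What to change.** Add to Aim 1 one descriptive safety table by randomised arm, with risk differences (SC-TF-CBT minus standard TF-CBT) and 95% confidence intervals:

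1. Children with an IE CGI-I rating of 7 or 8 at post-treatment, 6 or 12 months. Add week 6 only if the IE did rate then; Table 1 and 5.1.1.c need to be reconciled on this. Give the number rated in each arm and a sensitivity analysis for children with no IE rating.
2. Children meeting the full any-rater definition in 5.1.1.c, labelled supportive, with the number of rating opportunities by arm, since contact schedules differ.
3. New child suicidal ideation at the scheduled interviews.
4. Adverse events by grade and relatedness.

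Report the table beside any conclusion of comparability, and label it an estimate and not a powered test. The half-width is about 8 to 11 points if the any-rater rate is near the pilot figure; the narrower IE-only event has no documented rate, so its precision cannot be stated in advance. Label the table post hoc if outcome analysis is already done. Give the by-arm counts to the monitoring board only if its reviews are continuing.

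The cost is a paragraph and a table from data already collected. The downside is wide intervals that cannot exclude a moderate excess, and a claim of comparability that may read less favourably.
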